7.4. Validated Investigator Global Assessment

The vIGA is a global assessment of the current state of the disease. It is a 5-point morphological assessment of overall disease severity.

The vIGA (excluding hands and feet) will be assessed as specified in [Table 2](#).

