7.6. Patient-Oriented Eczema Measure

The Patient-Oriented Eczema Measure (POEM), developed by Charman et.al., ([Charman 2004](#)) is a self-assessment of disease severity by the participant. The POEM has a maximum value of 28 based on the participant's response to seven questions scored from 0 to 4.

The POEM will be assessed at the visits specified in [Table 2](#).

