9.3.1. Efficacy Analyses

The aims of the analyses of the primary endpoint – percent change from baseline at Week 4 in 7-day average of daily peak pruritus NRS – is to test for treatment effect, to characterize the gel concentration-response curve, and to estimate the minimum effective and optimal concentration. The Multiple Comparison Modelling (MCPMod) approach will be applied to the analyses.

Candidate gel concentration-response models which will be used in the analysis include the following:

- Linear model.
- Quadratic model with maximum effect reached at 3.5%, the model parameter is -0.1428571.
- Exponential model which reaches 20% of the effects at 2.5%, the model parameter is 1.803368.
- E_{max} model with $ED_{50}=2.5\%$.
- Sigmoid E_{max} model with $ED_{50}=2.5\%$ and Hill's parameter = 2.5.

[figure not shown]
- Logistic model which reaches 20% and 95% effects at concentrations 2.5% and 5%, respectively, the model parameters are $ED_{50\%} = 3.3002654$, $\delta = 0.5772694$.

The minimum effective concentration is defined as the lowest concentration whose standardized effect size is at least 0.25 and is significantly different from placebo at a 2-sided significance level of 0.2.

The optimal concentration is defined as the highest concentration of ASN008 used in this clinical trial without safety concerns for linear and exponential models, or the lowest concentration which maintains 90% of the maximum effect for the rest of candidate models.

Figure 3 depicts the shapes of curves for each candidate model, assuming the vehicle effect is 10% and treatment effect is 40% (30% improvement over vehicle).

Figure 3 Candidate Concentration - Response Models

Analysis of primary endpoint consists of the following steps:

Mean and variance estimation: A Mixed model repeated measures with visit, treatment, baseline disease severity, and visit by treatment interactive and fixed effects, baseline NRS as covariate, participant as random effects will be fitted first, the least-squares means and their variance-covariance matrix at Week 4 will be estimated using the fitted model.

1. MCP-step: the candidate models are tested using the estimated means and their variance-covariance matrix from the previous step. If any of the models is statistically significant at

2-sided significance level of 0.1, the treatment effect is established, the analysis moves to the next step.

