2. Mod-step: the concentration-response curve will be characterized, and the minimum effective concentration and optimal concentration will be estimated. All significant models indicated by the previous step will be fitted, and minimum effective concentration and optimal concentration will be estimated based on the fitted models.
3. Finally, weighted estimates for minimum effective concentration and optimal concentration will be calculated using weighing in Buckland et al. ([Buckland 1997](#)).

The above analysis will be performed on the modified intent-to-treat set and PP set; the modified intent-to-treat set will be used as the primary analysis set.

The change from baseline and percent change from baseline in Pruritus NRS will be analyzed using a mixed effects model with baseline pruritus NRS as covariate, treatment, visit, treatment by visit as fixed effects, participant as random effects. With fitted model, the least square means and their 95% confidence intervals, the least mean differences between each active treatment and placebo and their 95% confidence intervals will be calculated for Week 1, 2, 3, and 4.

The change from baseline and percent change from baseline in Pruritus NRS will also be summarized by treatment and visit using descriptive statistics.

The above analysis will be performed on the modified intent-to-treat and PP sets.

Pruritus response, which is defined as improvement (reduction) of 7-day average of daily hand peak pruritus NRS ≥ 4 from Baseline, will be analyzed using the Cochran Mantel Hansel test, controlling for NRS at baseline, at Week 1, 2, 3, and 4.

Pruritus response will also be summarized descriptively by treatment and visit.

Pruritus response will be analyzed on both the modified intent-to-treat and PP sets.

All other continuous variables will be analyzed in a similar manner as the percent change from baseline in Pruritus NRS; all other binary variables will be analyzed in a similar manner as the Pruritus response.

All efficacy variables will be listed for each participant by visit.

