## **1 INTRODUCTION**

This statistical analysis plan was drafted for the study protocol ASN008-201 “A Randomized, Double-Blind, Vehicle-Controlled, Phase 2 Trial to Evaluate the Anti-pruritic Efficacy, Safety, Tolerability, and Pharmacokinetics of ASN008 in Adults with Mild to Moderate Atopic Dermatitis”. In this document, the contents and methods of statistical analysis will be described in detail.

This statistical analysis plan was based on ASN008-201 Protocol Version 3.0, 05 July 2023 and Case Report Form version 8.0, 31 August 2023.

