Mean and variance estimation: A MMRM model with visit, treatment and visit by treatment interaction as fixed effects, baseline NRS as covariate, participant as random effects will be fitted first, the ls means and their variance-covariance matrix at Week 4 will be estimated using the fitted model.

1. MCP-step: the candidate models are tested using the estimated means and their variance- covariance matrix from the previous step. If any of the models is statistically significant at two-sided significance level of 0.1, the treatment effect is established, the analysis moves to the next step.
2. Mod-step: the concentration-response curve will be characterized, and the minimum effective concentration and optimal concentration will be estimated. All significant models indicated by the previous step will be fitted, and minimum effective concentration and optimal concentration will be estimated based on the fitted models.
3. Finally, weighted estimates for minimum effective concentration and optimal concentration will be calculated using weighing in Buckland et al. (Buckland 1997).

For MMRM model fitting, the unstructured (UN) variance-covariance matrix will initially be assumed. If the model does not converge using the UN covariance structure, the autoregressive (order 1) AR(1) structure will be used. If the AR(1) structure also does not converge, other covariance structures, such as the Toeplitz structure, deemed appropriate to fit the data will be used.

To estimate the degree of freedom, the Kenward Roger method will be used.

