## **13.2 Key Secondary Endpoints**

The following continuous secondary efficacy endpoints, as defined in [section 5.7](#), will be analyzed using MMRM model with visit, treatment and visit by treatment interaction as fixed effects, baseline NRS as covariate, participant as random effects will be fitted first, the ls means and their variance-covariance matrix at Week 4 will be estimated using the fitted model. Percent change of 7-day average daily peak pruritus NRS from Baseline to Week 1, 2, and 3.

- Change of 7-day average daily peak pruritus NRS from Baseline to Week 1, 2, 3 and 4.
- Change and percent change from baseline in daily peak pruritus NRS from Days 1 to 7.
- Change from baseline in 5-D Pruritus Scale at Week 2 and 4.
- Change and percent change from baseline in the EASI score at Week 2 and 4.
- Change from baseline in total BSA at Week 2 and 4.
- Change from baseline in the Dermatology Life Quality Index (DLQI) at Week 2 and 4.
- Change from baseline in The Patient Oriented Eczema Measure (POEM) at Week 2 and 4.

The endpoints will be summarized by visit presenting LS Mean, 95% CI and associated p-value from the above MMRM model, using mITT analysis set and PP set.

The following categorical secondary efficacy endpoints will be analyzed based on Fisher's exact test. In addition, odds ratio (OR) and 95% Wald confidence intervals will also be presented when applicable:

- Pruritus response is defined as the 7-day average of daily peak pruritus NRS reduction  $\geq 4$  points from Baseline at Week 1, 2, 3, and 4.

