## **15 CHANGES FROM PROTOCOL**

- Added “analyses of adverse events will include all events reported from the time of informed consent to 28 days after the last dose of study drug” to AE definition.
- Added “receive at least 1 dose of treatment” to the definitions of all the analysis sets.
- Updated the definition of the Per protocol population.
- Updated the analysis of categorical efficacy endpoints to use Fisher exact test instead of the CMH test.

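### The SAP drops baseline disease severity from the primary MMRM that feeds MCPMod, and its list of changes from the protocol does not record this

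*SAP*

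**What the plan says.** Protocol 9.3.1 sets out the primary analysis in steps. The first fits "A Mixed model repeated measures with visit, treatment, baseline disease severity, and visit by treatment interactive and fixed effects, baseline NRS as covariate", with participant as a random effect. The Week 4 least-squares means and their covariance matrix from that fit go into the MCP test and then the modelling step.

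SAP 13.1 describes the same step, followed by the same MCP, Mod and weighting steps, but fits "A MMRM model with visit, treatment and visit by treatment interaction as fixed effects, baseline NRS as covariate, participant as random effects". Baseline disease severity is absent.

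Other places that bear on this:

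- SAP Section 1: "This statistical analysis plan was based on ASN008-201 Protocol Version 3.0, 05 July 2023". This is the protocol version that contains the severity term, so the difference is not a leftover from an older text.
- SAP Section 15 lists four changes: the adverse event window, the at-least-one-dose requirement in the analysis sets, the per-protocol definition, and "Updated the analysis of categorical efficacy endpoints to use Fisher exact test instead of the CMH test". None concerns the MMRM.
- Later in protocol 9.3.1, a separate by-week analysis of change and percent change in NRS uses a "mixed effects model with baseline pruritus NRS as covariate, treatment, visit, treatment by visit as fixed effects". It has no severity term.
- SAP 13.2 uses the 13.1 model again for the continuous secondary endpoints: "MMRM model with visit, treatment and visit by treatment interaction as fixed effects, baseline NRS as covariate, participant as random effects".
- SAP Appendix 2 gives code for the candidate dose-response models but no MMRM formula.

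**The concern.** This one model drives the whole primary analysis. Its output decides whether any candidate shape is significant, and it underlies the minimum effective and optimal concentration estimates. SAP 13.1.2 reuses it for the sensitivity and per-protocol repeats. Its covariates should be fixed, and any departure from the protocol recorded, before unblinding.

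As the documents stand, an analyst could fit the model with or without severity and cite a document for either. The Fisher-for-CMH entry shows that Section 15 is used to log changes of analysis method, so a reader would expect a change to the primary model to appear there.

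The severity term is also undefined. Protocol 7.4 says of the vIGA: "It is a 5-point morphological assessment of overall disease severity". Protocol 7.6 says the POEM "is a self-assessment of disease severity by the participant". The vIGA is the more natural reading, because protocol 3.1 ties mild to moderate AD to vIGA 2 or 3, but the model text does not say so.

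Three things are at stake: pre-specification, a little precision, and adjustment for chance imbalance in severity. The last applies because neither document names a stratification factor for randomization.

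**Working it through.** **Comparison of the two models.**

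| Term | Protocol 9.3.1, primary step | SAP 13.1, same step |
|---|---|---|
| Visit, treatment, visit by treatment | yes | yes |
| Baseline NRS | yes | yes |
| Participant (random) | yes | yes |
| Baseline disease severity | yes | no |
| Removal listed in SAP Section 15 | – | no |

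**Reproducing the plan's figure.** Inputs from SAP 5.1 and protocol 9.1: difference 28.8 points, SD 40, 2-sided alpha 0.1, power 80%. The standardized effect is 28.8/40 = 0.72. The normal-approximation formula gives n = 24 per group with power 0.802, which matches the plan. No covariate enters that calculation, so the planned n does not depend on the severity term.

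**Size of the effect.** The documents do not say how much variance severity explains. Assumptions: severity is a two-level factor split 50/50, its levels differ by *e* = 10 to 20 points in percent change, and it is uncorrelated with baseline NRS.

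- Variance explained: R² = 0.25·e²/40². For e = 10, 25/1600 = 1.6%; for e = 20, 100/1600 = 6.3%.
- Residual SD: 40·√(1 − R²) = 39.69 (e = 10) or 38.73 (e = 20), so the SE falls by 0.8% or 3.2%.
- Unadjusted SE of a contrast with vehicle: 40·√(2/n) = 11.55 at n = 24 and 10.33 at n = 30.

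Pairwise power for 28.8 points at 2-sided 0.1, using the noncentral t with four-arm degrees of freedom (which is why it starts at 0.797 and not 0.802):

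| n per arm | No severity term | e = 10 | e = 15 | e = 20 |
|---|---|---|---|---|
| 24 | 0.797 | 0.802 | 0.809 | 0.819 |
| 30 | 0.870 | 0.875 | 0.881 | 0.888 |

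Power of the MCP test was simulated at n = 24. The settings were the six stated shapes with Hill parameter 2.5, a maximum effect of 28.8 points, and the maximum contrast statistic at one-sided 0.05, taken as the equivalent of 2-sided 0.1. By true shape, power is about 0.79 to 0.84 without the term, 0.80 to 0.85 at e = 10, and 0.82 to 0.86 at e = 20.

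**Chance imbalance.** With a 50/50 factor and simple randomization, exact binomial probabilities of a difference from vehicle of at least 20 percentage points in severity mix are:

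- one given active arm: 0.193 (n = 24), 0.155 (n = 30);
- any of the three: 0.421 (n = 24), 0.348 (n = 30).

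An imbalance of exactly 20 percentage points shifts the unadjusted contrast by 0.2·e = 2 to 4 points, in either direction. Relative to the SE this is 2/11.55 = 0.17 to 4/11.55 = 0.35 at n = 24, and 2/10.33 = 0.19 to 4/10.33 = 0.39 at n = 30.

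**Post hoc choice.** If the more favourable of the two models were picked after the fact, a single one-sided 0.05 test would run at about 0.055 (e = 10) to 0.060 (e = 20). This treats the two test statistics as correlated at √(1 − R²).

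**The case against.** The strongest reply is that this is a documentation gap with little effect on the result. There is no bias, baseline NRS remains in the model, and the sample size is untouched. Protocol 9.3 leaves further analytic detail to the SAP. SAP 13.1 gives a model that can be run, with a covariance fallback and Kenward-Roger degrees of freedom, whereas the protocol's version cannot be run as written because its severity term is undefined. Eligibility already restricts vIGA to 2 or 3, no stratification requires the term, and the protocol's own by-week NRS model omits it. On this view, logging the removal is as good as restoring the term. The magnitude inputs are also assumptions, and they lean high: if severity correlates 0.5 with baseline NRS, the SE reduction falls to about 0.6 to 2.4%.

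Much of this stands. The effect is small, the inputs are not from the documents, and removal could be defended. But adding detail is different from deleting a named term from the primary model. The by-week model is a separate analysis; protocol 9.3.1 gives the model that feeds MCPMod in its own step, and severity is in it. Neither document says which prevails in a conflict. That the term is undefined is a reason to settle it now.

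**Conclusion.** The point holds. SAP 13.1 departs from protocol 9.3.1 on the covariates of the primary model, and SAP Section 15 does not declare it. The correction should be made, although the numerical consequence is modest: an SE reduction of 0.8 to 3.2%, a gain in pairwise power of at most about 0.02, and a shift of 0.17 to 0.39 SE in a contrast if a 20-percentage-point severity imbalance occurs. These sizes rest on an assumed 50/50 two-level factor with a 10 to 20 point gap, uncorrelated with baseline NRS. The textual discrepancy rests on no assumption. Either model, fixed in advance, gives a valid test. The weakness is that two are on file.

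**What to change.** Before unblinding, take one of two routes.

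1. Preferred: add baseline disease severity as a fixed effect to the MMRM in SAP 13.1, as protocol 9.3.1 has it, and carry it into the sensitivity and per-protocol repeats in 13.1.2. State the variable, visit and coding. Day 1 vIGA (2 versus 3) is a natural choice, but the sponsor must specify it.
2. If the removal was intended, list and justify it in SAP Section 15, and keep the severity-adjusted MMRM as a sensitivity analysis.

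In the same revision, correct the response definition in the second paragraph of SAP 13.1. It refers to change from baseline, while SAP 5.1 and 13.1.1 use percent change. This is a wording fix only.

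The first route costs one model term (1 degree of freedom if two-level) and its definition. The second costs one entry in Section 15 and one extra run. Neither needs new data if severity comes from an assessment already scheduled on Day 1.

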## 5 GENERAL CONSIDERATIONS

### 5.1 Sample Size

For the primary endpoint analysis of the percent change of 7-day average daily peak pruritus NRS from Baseline to Week 4, N = 24 / group will give us 80% power to detect a standardized effect of 0.72 with 2-sided significance level of 0.1 (28.8% improvement over placebo in % change from baseline in pruritus, assuming standard deviation [SD] = 40%).

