### 13.1 Primary Efficacy Endpoint

The aims of the analyses of the primary endpoint, percent change from baseline at Week 4 in daily peak pruritus NRS, are to test for treatment effect; to characterize the gel concentration-response curve; to estimate the minimum effective and optimal concentration. The MCPMod approach will be applied for this study. If any candidate model given below is significant, the significant treatment effect will be concluded, then the significant models will be used to estimate the minimum and optimal concentration.

In essence, the aim of the primary analysis is to establish the ASN008 gel concentration-response curve, the response is defined as the change from baseline in 7-day average of the daily peak pruritus NRS at Week 4 for mild and moderate atopic dermatitis participants who do not use any prohibited medications during the entire study and have no safety concerns. For the primary analysis, any data after use of the prohibited medication will set to missing values. The missing data will be imputed implicitly using MMRM modeling under assumption of missing at random.

For the MCPMod approach, the candidate gel concentration-response models to be applied are given follows:

[figure not shown]
- Linear model.
- Quadratic model with maximum effect reached at 3.5%, the model parameter is - 0.1428571.
- Exponential model which reaches 20% of the effects at 2.5%, the model parameter is 1.803368.
- $E_{max}$  model with  $ED50 = 2.5\%$ .
- Sigmoid  $E_{max}$  model with  $ED50=2.5\%$  and Hill's parameter = 2.5.
- Logistic model which reaches 20% and 95% effects at concentrations 2.5% and 5%, respectively, the model parameters are  $ED50\% = 3.3002654$ ,  $\delta = 0.5772694$ .

The minimum effective concentration is defined as the lowest concentration whose standardized effect size is at least 0.25 and is significantly different from placebo at a 2-sided significance level of 0.2.

The optimal concentration is defined as the highest concentration of ASN008 used in this clinical trial without safety concerns for linear and exponential models, or the lowest concentration which maintains 90% of the maximum effect for the rest of candidate models.

Figure 2 depicts the shapes of curves for each candidate model, assuming the vehicle effect is 10% and treatment effect is 40% (30% improvement over vehicle).

Figure 2 Candidate Concentration - Response Models

Analysis of primary endpoint consists of the following steps:

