## Appendix 2: Sample R Codes for Primary Analysis

R version 4.3.1 and “sas7bdat”, “dplyr”, “DoseFinding”, “MCPMod”, “mmrm”, “nlme”, “lme4” packages will be used to generate the outputs:

Model parameters:

For the MCPMod approach, the candidate gel concentration-response models to be applied are given follows:

- Linear model
- Quadratic model with maximum effect reached at 3.5%, the model parameter is - 0.1428571
- Exponential model which reaches 20% of the effects at 2.5%, the model parameter is 1.803368
- Emax model with ED50 = 2.5%
- Sigmoid Emax model with ED50=2.5% and Hill's parameter = 2.5
- Logistic model which reaches 20% and 95% effects at concentrations 2.5% and 5%, respectively, the model parameters are ED50% = 3.3002654, delta = 0.5772694

Specify model parameters as following:

```
quad<-guesst(d=3.5,p=1,"quadratic")
exp<-guesst(d=2.5,p=0.2,"exponential",Maxd=5)
emax<-guesst(d=2.5,p=0.5,"emax")
sigemax<-guesst(d=c(1.25,2.5),p=c(0.2,0.5),"sigEmax")
logis<-guesst(d=c(2.5,5),p=c(0.2,0.95),"logistic")
models<-Mods(linear=NULL,quadratic=quad,exponential = exp,emax=emax,sigEmax
=sigemax,logistic=logis,doses=c(0,1.25,2.5,5))
```

The optimal concentration is defined as the highest concentration of ASN008 used in this clinical trial without safety concerns for linear and exponential models, or the lowest concentration which maintains 90% of the maximum effect for the rest of candidate models.

Optimal concentration:

```
ED(fit,0.9)
```

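### The primary MCP-step rule is two-sided with no direction, so a model significant for worse itch formally establishes the treatment effect and feeds the concentration estimates

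*SAP*

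**What the plan says.** Both documents use the MCP step as the test of treatment effect. SAP 13.1: "If any of the models is statistically significant at two-sided significance level of 0.1, the treatment effect is established". Protocol 9.3.1: "2-sided significance level of 0.1, the treatment effect is established, the analysis moves to the next step". SAP 13.1 also states the consequence: "If any candidate model given below is significant, the significant treatment effect will be concluded", and the significant models are then used to estimate the minimum effective and optimal concentrations.

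The later rules in SAP 13.1 are:

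- **Minimum effective concentration:** the lowest one with a standardized effect of at least 0.25 that "is significantly different from placebo at a 2-sided significance level of 0.2".
- **Optimal concentration, linear and exponential models:** the highest concentration studied that is free of safety concerns.
- **Optimal concentration, other models:** the lowest concentration that keeps 90% of the maximum effect.

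On sign, SAP 5.4 defines percent change as post-baseline minus baseline over baseline, so improvement is negative. The text introducing the candidate-curve figure in SAP 13.1 gives effects as positive improvements (10% vehicle, 40% treatment). The SAP Appendix 2 code builds the candidates ("models<-Mods(linear=NULL,quadratic=quad,exponential = exp" and so on) with no stated direction, and shows no test call.

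**The concern.** The objective is an anti-pruritic effect compared with vehicle, and the sample size is justified by an improvement over placebo. The decision rule carries neither idea. Followed literally, a contrast significant for more itch establishes the effect, and the corresponding model goes on to concentration estimation. For a linear or exponential fit, the plan then names the highest concentration without safety concerns, whichever way the curve slopes. For the other models, 90% of the maximum effect under a worsening fit would be 90% of the maximum worsening.

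The case is not far-fetched for a topical gel. The local tolerability scale (protocol 8.1.6) scores itching, stinging and burning. In Phase 1 the participants with atopic dermatitis received 2.46% (protocol 1.1), so 5% is a new strength in this population. If such a result occurred, setting it aside would be an unplanned departure from the primary rule.

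**Working it through.** **Inputs.** From the documents: 24 per group, standardized effect 0.72 (28.8/40), 80% power and two-sided 0.1 (SAP 5.1); about 30 per arm and 1:1:1:1 allocation (protocol synopsis); six candidate shapes on 0, 1.25, 2.5 and 5% (SAP 13.1, Appendix 2). Assumed: equal SD, complete Week 4 data in place of the MMRM covariance matrix, and a multiplicity-adjusted maximum-contrast test. MCPMod implies that adjustment, but the documents do not spell it out.

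**1. Reproduce the stated sample size.** n = 2(z₀.₉₅ + z₀.₈₀)²/0.72² = 2(1.645 + 0.842)²/0.5184 = 23.9, so 24 per group; power at 24 is 80.2%. Two-sided 0.1 and one-sided 0.05 both use z = 1.645, so the formula gives 24 either way.

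**2. Critical value of the planned test.** Optimal contrasts for the six shapes with pooled variance on 4n − 4 degrees of freedom were simulated. The critical value is about 1.99 at n = 24 and 1.98 at n = 30, and is the same for two-sided 0.1 and one-sided 0.05 within simulation error. With no effect, the two-sided rule rejects 5.0% towards improvement and 5.0% towards worsening.

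**3. Only the 5% gel worsens itch, by 0.5 SD, n = 30.** With improvement coded positive, the exponential shape exp(d/1.803368) − 1 takes the values 0, 1, 3, 15. Subtracting the mean 4.75 and dividing by √144.75 = 12.03 gives the contrast (−0.395, −0.312, −0.145, 0.852). The expected statistic is √30 × 0.852 × (−0.5) = −2.33, beyond −1.98. Over all six models, the rule is met through worsening in about 67% of simulated trials.

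**4. Mixed case: improvements of 0.4, 0.3 and −0.4 SD at 1.25, 2.5 and 5%, n = 30.**

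- Exponential: √30 × (−0.312×0.4 − 0.145×0.3 − 0.852×0.4) = 5.477 × (−0.509) = −2.79.
- Linear, contrast (−0.592, −0.254, 0.085, 0.761): 5.477 × (−0.102 + 0.026 − 0.304) = −2.08.

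The rule is met through worsening in about 80% of trials and through benefit in about 3%. Significance for worsening by model: exponential 79%, linear 54%, sigmoid Emax 52%, Emax 18%. Among trials that meet the rule through worsening, exponential and/or logistic are the only significant models in 31%; in the other 69% at least one further model joins.

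**5. Linear worsening at n = 24.**

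| Worsening at 5% | Rule as written met | One-sided 0.05 for improvement met |
|---|---|---|
| 0.25 SD | 22% | 0.7% |
| 0.36 SD | 34% | 0.2% |
| 0.50 SD | 53% | 0.06% |

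**6. Power for true improvement, maximum 0.72 SD, n = 24.**

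| True shape | Two-sided 0.1 | One-sided 0.05 |
|---|---|---|
| Linear | 79.7% | 79.8% |
| Quadratic | 80.4% | 80.4% |
| Exponential | 83.2% | 83.2% |
| Emax | 79.5% | 79.5% |
| Sigmoid Emax | 82.5% | 82.6% |
| Logistic | 84.3% | 84.3% |

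The two-sided mean is (79.7 + 80.4 + 83.2 + 79.5 + 82.5 + 84.3)/6 = 81.6%. At n = 30 the range is 87.0 to 91.0% both ways.

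**7. Orientation.** If the one-sided test were pointed at an increase while improvement is coded negative, its power at 0.72 SD would be under 0.04% for every shape.

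**The case against.** The strongest reply is that the intended direction is clear from context. SAP 5.1 describes the planning effect as "28.8% improvement over placebo in % change from baseline in pruritus, assuming standard deviation [SD] = 40" percent, and SAP 13.1 describes its curves as improvement over vehicle. Read that way, a standardized effect of at least 0.25 means improvement, and a worsening gel would get no minimum effective concentration. That reading is fair, so a reader should not infer that nothing in the plan points to benefit. It does not reach the MCP-step rule or the linear and exponential optimal rule.

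Second, irritation at 5% might trigger the safety condition, since confirmed intolerance is reported as an adverse event (protocol 8.1.6). It might, but safety concerns are not defined for this rule, and a higher peak-itch score need not be recorded as intolerance.

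Third, the harm would be seen. Protocol 9.3.1 plans least-squares mean differences of each active arm from placebo with 95% intervals. In 99.5% of the mixed-case trials that met the rule through worsening, the observed 5% mean was worse than vehicle. This stands: it would be wrong to infer that harm would pass unnoticed. What remains is that the primary rule would still declare success.

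Fourth, two-sided testing with direction read from the estimates is common, and the false-positive rate for benefit is already 5%. Also true. The plan omits the sentence that says direction is read that way.

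Finally, Appendix 2 is sample code with no test call, so its silence on direction shows incompleteness, not a choice.

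**Conclusion.** The point holds as a defect in the written primary decision rule. A model significant for worse itch establishes the treatment effect and enters the Mod step, and the linear and exponential optimal rule does not restore a direction. The minimum effective concentration rule is also written two-sided, though its effect may be read as improvement.

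The size is 5% of trials under no effect, about 67% and about 80% in the two n = 30 scenarios. Those scenarios are illustrations, not predictions, and rest on the assumptions listed with the inputs. The sample size is unaffected.

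Two stronger inferences are not supported. One is that the exponential and logistic models alone would feed the concentration estimates in the mixed case; linear and sigmoid Emax often join them. The other is that a directional test would rescue the low-concentration benefit; success for benefit there is about 3% under either test.

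**What to change.** In SAP 13.1 and protocol 9.3.1:

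- Test each candidate one-sided at 0.05, multiplicity-adjusted, for a greater reduction in NRS than vehicle, and admit only models significant in that direction to the Mod step.
- Require improvement over vehicle in the minimum effective concentration rule, at one-sided 0.1.
- State the sign convention in the text and in the Appendix 2 code, and show the test call. Either analyse percent reduction, or define the contrasts for a decrease, because SAP 5.4 makes improvement negative.

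The cost is wording and a small code addition. The 24 per group, the critical value, the 5% error rate for benefit and the power for the six assumed shapes stay as they are. The equivalence is with one-sided 0.05; one-sided 0.025 would lose power. A worsening trend would be reported through the planned differences from vehicle instead of through the success rule.
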